All patients will undergo a LGE-MRI within 30 days prior to the ablation procedure. The clinical purpose of the initial MRI is to define the anatomy of the heart chambers as well as the vessels for procedure planning. For research purposes, we will use this initial clinical MRI to delineate atrial structural remodeling or fibrosis to be used during the procedure in patients randomized to group 2 (pulmonary vein isolation + scar-based ablation) and for later analysis in all patients.

Imaging is done at our institution and will be reviewed for quality by the study staff. LGE-MRI sequences that do not meet quality standards for fibrosis analysis will not be further processed and these patients will be excluded from the study. Subjects for whom images are successfully evaluated will be randomized to the study groups.

This will be followed by block randomization in 1:1:1 format to a) pulmonary vein isolation (PVI) only (current standard of care), b) PVI plus targeting of dense LGE sites, which are confirmed on bipolar mapping to have voltage <0.1 mV, and c) PVI plus targeting of rotor anchor sites predicted by modeling.

At baseline, all patients will be evaluated for their quality of life (QOL) using the Short-form health survey (SF-36) (Ware & Sherbourne, 1992) for overall as well as AF-related impact on quality of life (Refer to additional study documents). The severity of symptoms will be tested using the European Heart Rhythm Association (EHRA) score of atrial fibrillation and the Canadian Cardiovascular Society (the CCS-SAF) scale (Dorian et al., 2006). Clinical data will be stored electronically and linked to a specific research ID number. Information linking de-identified data to the patients will be stored in the locked research office, in a password-protected file. Only members of the research team, in charge of collecting clinical information, will have access to this file. Individual subject binders containing signed consent forms and clinical source documentation will be labeled using study subject numbers and stored in the locked research office mentioned previously.

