Prior to ablation, patients will be asked to complete 7 days of twice-daily 1-minute rhythm monitoring using the AliveCor® device. After the procedure, follow-up will be done on a weekly basis through trans-telephonic transmissions of ECG recordings. Periodic reminders will be sent to patients (via telephone, email, or mail) regarding follow up transmissions in the event that a weekly transmission is missed. Although preferred, it is not imperative that all patients complete all weekly follow up transmissions. In addition, study participants will be advised to provide recordings if they experience heart-related symptoms (palpitations, shortness of breath, rapid heartbeat, chest pain). This extensive rhythm monitoring protocol is not standard of care and is done for research purposes. Review of the rhythm monitoring data will be performed in accordance with current clinical guidelines. The device software and the investigators will analyze rhythm strips and a report will be available to the research team and to the treating physician upon his/her request.

In addition, upon detection of any arrhythmia with important clinical implications, the investigators will notify the electrophysiologist involved in the care of the patient. The research team may contact the patient directly if prompt action is advised, such as reporting to the local emergency room or following up with their electrophysiologist. The rhythm monitoring protocol utilized in this study may result in unscheduled visits to the physician. If a repeat ablation procedure is indicated, it will be scheduled according to standards of clinical care.

A detailed study timeline is attached at the end of the document.

b. Study duration and visits.

We aim to complete the proposed study protocol in two years. After the ablation, patients will be followed at 3, 6 and 12 months via in clinic visit; a 1 month and 9 month follow up will take place via remote ECG transmission. Follow-up research questionnaires and post-ablation MRI will be scheduled to coincide with the routine clinical visits. Hence, no additional visits will be required of research participants unless it was not possible to schedule the MRI on the same day as clinic visits. Only then will we ask participants to present to JHH for the follow-up MRI.

c. Blinding, including justification for blinding or not blinding the trial, if applicable.

N/A

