d. Justification of why participants will not receive routine care or will have current therapy stopped.

N/A

e. Justification for inclusion of a placebo or non-treatment group.

N/A

f. Definition of treatment failure or participant removal criteria.

N/A

g. Description of what happens to participants receiving therapy when study ends or if a participant's participation in the study ends prematurely.

N/A

5. Inclusion/Exclusion Criteria

a. Inclusion Criteria

Patients are eligible for the SIMPlE AF study if they are 18-100 years of age, have a history of persistent atrial fibrillation, are indicated for an AF ablation procedure, and agree to participate in the SIMPlE AF trial.

b. Exclusion Criteria

- . Are unable or unwilling to provide informed consent for the SIMPlE AF study
- . Patients with cardiac devices like pacemakers, internal cardiac defibrillators and Cardiac Resynchronization Therapy Device (CRT). Patients with acute or chronic renal insufficiency (glomerular filtration rate <30 ml/min/1.73 m²), or patients in the perioperative liver transplantation period
- . Pregnant women
- . Patients who are unable to adhere to the follow up protocol

- . Patients with contraindication to MRI, including ferromagnetic aneurysm clips, metal in the eye, and implanted ferromagnetic or other MRI-incompatible devices
- . Patients in whom the LGE Cardiac MRI does not meet quality standards for fibrosis analysis
- . Subjects without daily access to a smart phone or tablet compatible with the AliveECG application and ability to upload ECG tracings for the follow up period
- . Patients with a history of allergic reactions to gadolinium-based contrast agents or ingredients and will not be premedicated**

****Subjects with a history of reaction to contrast may be premedicated according to institutional protocol prior to receiving intravenous contrast agents**

6. Drugs/ Substances/ Devices

- a. The rationale for choosing the drug and dose or for choosing the device to be used.

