Patients undergoing MRI angiogram are routinely injected with gadolinium as contrast. Gadolinium-based MRI contrast agents are used to visualize scar/ablation lesions in the atrial wall (McGann et al., 2014). Gadolinium chelates used as intravenous contrast media are extremely safe in patients with normal kidney function and do not exhibit the nephrotoxicity associated with iodinated media. Minor reactions including nausea and hives may occur in a small percentage of cases. Severe anaphylactic reactions are extremely uncommon (Runge, 2001).

- b. Justification and safety information if FDA approved drugs will be administered for non-FDA approved indications or if doses or routes of administration or participant populations are changed.

Gadolinium (total dose of 0.2 mmol/kg) will be administered 10 minutes prior to delayed enhancement imaging to evaluate for the presence of myocardial scar. Gadolinium-based contrast agents are not FDA-approved for diagnosis of cardiac disease by MRI. However, these agents have been routinely used for more than 10 years at the JHH and other centers for clinical and research purposes to evaluate diseases of the myocardium and vessels (Akoum & Marrouche, 2014) (Zareian et al., 2015). The standard gadolinium dose at JHH and other institutions in cardiac MRIs is a maximum of 0.2 mmol/kg.

- c. Justification and safety information if non-FDA approved drugs without an IND will be administered. N/A

7. Study Statistics

- a. Primary outcome variable.

Data from AliveCor® Mobile ECG rhythm device recordings, follow-up visits (examinations and ECGs), and QOL/follow-up questionnaires will be used to identify the success rates of the procedure. Procedure failure is defined as symptomatic or asymptomatic AF/Atrial flutter/Atrial tachycardia of at least 30 seconds duration that is documented by an ECG or device recording system, occurring after the 3-month blanking period following catheter ablation. Individually tailored ablation strategies for suppression of persistent AF have not been investigated. We hypothesize that individually tailored ablation strategies will improve AF/AT suppression compared to PVI alone. The association of time to AF/AT recurrence with ablation strategy will be examined in 30 randomized patients.

- b. Secondary outcome variables.

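### No masking to arm is specified for the readers of the primary-endpoint recordings, no rule says which reading decides, and the scoring of a repeat ablation during blanking is left implicit

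*Combined protocol and SAP*

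**What the plan says.** **Endpoint.** Section 7a defines procedure failure as AF, flutter or atrial tachycardia lasting at least 30 seconds, with or without symptoms, "documented by an ECG or device recording system, occurring after the 3-month blanking period following catheter ablation".

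**Reading.** Section 4a states: "The device software and the investigators will analyze rhythm strips and a report will be available to the research team". On the standard to be used it says: "Review of the rhythm monitoring data will be performed in accordance with current clinical guidelines". Section 4c, headed "Blinding, including justification for blinding or not blinding the trial, if applicable", is answered N/A. Section 4a also provides for coded data: "Clinical data will be stored electronically and linked to a specific research ID number".

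**Repeat ablation.** Section 4a foresees it: "If a repeat ablation procedure is indicated, it will be scheduled according to standards of clinical care". Neither section 7a nor the statistical plan in 7c mentions it. Section 4f, "Definition of treatment failure or participant removal criteria", is answered N/A.

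**Recording.** Section 4a asks for weekly transmissions and for extra strips when symptoms occur, but adds: "Although preferred, it is not imperative that all patients complete all weekly follow up transmissions".

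**Use of the results.** Sections 1 and 11 describe the 30 patients as the source of preliminary outcome data for a multicenter trial of 300.

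**The concern.** The operator necessarily knows which ablation was done, so the practical place to protect this endpoint is the reading of the recordings. Section 7a states the investigators' hypothesis that tailored ablation will do better than PVI alone, and section 4a has the investigators read the strips. If borderline strips were judged differently by arm, the recurrence estimates would separate without any true difference. Each patient has up to 39 scheduled strips after blanking, and one positive strip makes a failure, so a small per-strip difference accumulates.

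The repeat-ablation point is separate. A patient who needs a second procedure within three months and then stays free of AF has had more than the assigned strategy, yet the outcome is credited to that strategy. The plan does not acknowledge this choice. If some analysts also restarted the blanking period at the second procedure, the same patient could be scored in two ways.

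What is at stake is mainly the set of arm-level estimates that would inform the larger trial.

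**Working it through.** **1. Is a masked reader or a deciding reading specified anywhere?** Section 4a names two readers (software and investigators) and a general standard (clinical guidelines). Section 4c gives N/A. Sections 7a to 7c say nothing about readers. So no masking is specified and no order of precedence is given. The documents do not state that the readers know the arm.

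**2. How does section 7a treat a repeat ablation?** The definition depends only on a documented arrhythmia after blanking.
- Repeat after documented post-blanking AF: already a failure, so there is no gap.
- Repeat during blanking, then AF: a failure, provided blanking is counted from the first procedure. If blanking restarts, the date or even the status can change.
- Repeat during blanking, then no AF: a success by default.

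Repeat-ablation frequency is not given. As an illustration, take an arm with 5 of 10 patients AF-free, one of them re-ablated during blanking. It scores 5/10 = 50% under the default and 4/10 = 40% if that patient counts as a failure.

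**3. Size of a reading difference: false positives.** Inputs:
- Scheduled strips after blanking: 52 − 13 = 39 (weekly monitoring in 4a, 3-month blanking in 7a, 12-month follow-up).
- Recurrence 50% (7b gives about 50% suppression).
- Assumed: 35 of 39 strips sent, per-strip over-reading rate f, and over-reading in one arm only.

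An AF-free patient is scored a failure with probability 1 − (1 − f)^35. The arm shift is 0.5 times this, since only the AF-free half can be falsely turned into failures.

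| f | AF-free patients scored as failures | Shift in that arm |
|---|---|---|
| 0.1% | 3.4% | 1.7 points |
| 0.2% | 6.8% | 3.4 points |
| 0.5% | 16.1% | 8.0 points |

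With 29 strips the middle column is 2.9%, 5.6% and 13.5%; with 39 strips it is 3.8%, 7.5% and 17.8%. If f is the same in every arm, the gap between arms is zero.

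**4. Size of a reading difference: missed AF.** Assume onset spread evenly over the post-blanking weeks, 90% of strips sent, and visit ECGs at 6 and 12 months counted after onset. Missing 10% of true AF strips in one arm then gives 1.1, 1.5, 1.2 and 0.4 points at AF burdens of 2%, 5%, 10% and 30%. Missing 20% gives 2.3, 3.2, 2.6 and 0.8 points. Both are zero for continuous AF, because later strips catch it.

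**5. Against the noise.** At 10 per arm and 50% success, the standard error of a difference between two arms is √(2 × 0.5 × 0.5 / 10) = 0.22, or about 22 points.

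**6. Effect on the log-rank test.** Simulated false-positive rates, two arms of 10 with equal true recurrence of 50%, 2,500 runs per cell, at 5% and 30% burden:
- no reading difference: 3.9% and 5.8%
- f = 0.2% in one arm: 5.8% and 5.7%
- f = 0.5% in one arm: 8.4% and 7.9%

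The simulation error is about √(0.05 × 0.95 / 2,500) = 0.4 points near 5%. Only f = 0.5% clearly departs from the no-difference cells, at about 7% to 9% once simulation error is allowed for.

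**The case against.** The strongest reply is that the endpoint is fairly objective and the likely effect small. Software reads every strip, the threshold is a fixed 30 seconds, and all arms share the same device, schedule, reminders and visit ECGs. Every input to the size calculation except the 50% is assumed, and most plausible gaps are about 0.4 to 3.4 points against a standard error near 22. This stands as a limit on weight. It does not remove the gap: investigators also read, nothing says whose reading prevails, and a systematic shift is not reduced by adding patients if the same reading procedure is carried into the larger trial.

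Four stronger readings are tempting, and the documents do not support them.
- *That the strips are read by people who know the arm.* The text shows only that masking is not specified.
- *That a repeat ablation in blanking has no scoring rule.* Section 7a supplies a default (success if AF-free afterwards), and the N/A in 4f adds little because 7a holds the failure definition. What is missing is an explicit statement and the blanking clock. Other conventions exist, so scoring it as a failure in the primary analysis would be a trade-off and not a correction.
- *That optional weekly transmissions bias the comparison.* This concerns detection, not reading. Reminders, the adherence and upload exclusions and common visit ECGs reduce the risk, and no difference by arm is shown. A table of strips by arm is a reporting preference.
- *That repeat-ablation scar spoils the 1-year MRI analysis.* Section 7b compares patients with and without suppression, and scar from any procedure is part of the exposure measured.

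**Conclusion.** The point holds as a gap in specification that is cheap to close. No masking of the endpoint reader is specified and no reading is given precedence, so the recurrence estimates can be biased by reading; nothing in the documents shows that they would be. With 50% recurrence from section 7b and all else assumed, over-reading of 0.1% to 0.5% per strip confined to one arm shifts that arm by 1.7 to 8.0 points, and equal reading gives no shift. A reader might infer that the significance test is compromised. At 10 per arm it is little affected, except at 0.5% one-arm over-reading (about 7% to 9% false positives).

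The repeat-ablation point is narrower: the default in 7a credits the assigned strategy with a success achieved after a second procedure in blanking, and the blanking clock is not defined. One such patient is one of about ten in an arm. How many there would be is unknown.

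**What to change.** 1. **Sections 4c and 7a.** State that the endpoint reading of strips and ECGs is made by the existing investigators from files coded by research ID with the arm removed, where possible by one who did not perform that patient's ablation. State that this masked reading decides, with the software result recorded beside it. Clinical alerts stay as they are.
2. **Section 7a, for analysis only.** State that blanking is counted from the first ablation. Add one sensitivity analysis that scores a repeat left atrial ablation during blanking as a failure at the end of blanking. When to repeat an ablation is not touched.
3. **Optional.** Tabulate strips sent by arm.

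**Cost.** A few sentences, a coded export, one short extra analysis, and reader time for up to about 39 × 30 = 1,170 scheduled strips plus symptom strips and ECGs. Masking will be imperfect where the reader already knows the patient, for instance from handling an alert. The documents do not say how many investigators there are, so a reader with no other role in a patient's care cannot be assumed; hence the wording "where possible" in plain terms rather than a strict requirement.

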During ablation, the spatial coordinates and electrogram characteristics of >200 intra-cardiac points are sequentially sampled and saved. We hypothesize that sites with slow conduction during sinus rhythm,

representing AF substrates, are detectable as sectors with intermediate LGE intensity [image intensity ratio (IIR) 0.9-1.6] on LGE-CMR. We will co-register the spatial coordinates of sites exhibiting slow conduction with pre-procedural LGE-CMR for 30 patients. We will then compare the baseline image intensity ratio of sites with slow conduction versus other sites.

Catheter ablation results in long-term AF suppression in approximately 50% of patients with persistent AF. We hypothesize that AF suppression at 1-year will be associated with the presence of IIR>1.6 at the 1-year LGE-CMR in sectors where slow conduction was observed at baseline. We will co-register the baseline spatial coordinates of sites exhibiting slow conduction with 1-year post-procedural LGE-CMR images for 30 patients randomized to ablation. We will then compare the 1-year image characteristics of sectors with slow conduction among patients with and without AF suppression at 1-year follow-up.

Catheter ablation promotes scar formation and more extensive ablation strategies may adversely affect left atrial function. However, AF recurrences and continuation of antiarrhythmic drug therapy may also lead to progression of atrial and ventricular dysfunction. We hypothesize that more extensive patient tailored approaches will have less negative impact on atrial and overall cardiac function. We will measure the change (baseline to 1-year MRI) in left atrial and left ventricular regional and global strain in 30 randomized patients. We will then examine the association of the change in regional and global strain with ablation strategy.

- c. Statistical plan including sample size justification and interim data analysis.

Based on the variable success rate of 40-80% in AF ablation, we anticipate that the study cohort of 30 patients would produce adequate sample size in all treatment arms and be sufficient to make meaningful statistical comparison.

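### Blinding is entered as N/A and nothing else masks the MRI measurements, so all three secondary objectives are open to reading bias of unknown size

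*Combined protocol and SAP*

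**What the plan says.** Section 4c ("Blinding, including justification for blinding or not blinding the trial, if applicable") is answered N/A, with no reason given.

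On who handles the data, section 4a states: "Imaging is done at our institution and will be reviewed for quality by the study staff". It adds: "Subjects for whom images are successfully evaluated will be randomized to the study groups". The baseline scan is also "to be used during the procedure in patients randomized to group 2", and is kept for later analysis in all patients. For rhythm: "The device software and the investigators will analyze rhythm strips and a report will be available to the research team".

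Section 7b gives each secondary objective an MRI measurement:

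- **Slow-conduction substrate.** "We will co-register the spatial coordinates of sites exhibiting slow conduction with pre-procedural LGE-CMR for 30 patients". Then: "We will then compare the baseline image intensity ratio of sites with slow conduction versus other sites". The expected result is an image intensity ratio (IIR) of 0.9-1.6 at slow sites.
- **Post-ablation scar.** The plan will "compare the 1-year image characteristics of sectors with slow conduction among patients with and without AF suppression at 1-year follow-up". The expected result is IIR above 1.6 in those sectors when AF is suppressed.
- **Remodelling and function.** Change in left atrial and left ventricular strain from baseline to 1 year is related to ablation strategy, and the tailored arms are expected to fare better.

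No section mentions a masked reader, a core laboratory, a second reader, a locked reading or a masked co-registration step.

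**The concern.** In each secondary objective the measurement and the label it is compared against can be known to the same small team. The hypothesised direction is also written into the plan. Alignment, sector definition and contouring may involve judgement, since the documents do not say that any of them is automated. If judgement leans with the label, the lean has the same form as the hypothesised association. The methods in section 7c (chi-square, rank-sum, log-rank, Cox, t-test) cannot separate the two afterwards. The results matter beyond this cohort, because the 30-patient data are meant to lead to a 300-patient multicentre trial.

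**Working it through.** The plan has no figure of its own to reproduce here. It gives no reader error, no SD and no effect size for any MRI measure. The check has two parts.

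**1. Which label each reading must be protected from**

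| Objective | Measurement | Label compared | When the label exists | Protection in the plan |
|---|---|---|---|---|
| 1 | Co-registration, then baseline IIR | Slow vs other electrogram site | From ablation | None stated |
| 2 | 1-year LGE in slow-conduction sectors | AF suppressed or not | During follow-up | None stated |
| 3 | Change in strain | Ablation strategy | From randomisation | None stated |

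Baseline images are checked before randomisation, but section 4a describes that step as a quality check. It does not say that IIR or strain is measured or locked then. IIR at slow-conduction sites could not be locked then in any case, because the sites are sampled during ablation.

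**2. What a label-dependent shift would do**

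Inputs from the documents: 30 patients, 1:1:1 allocation (about 10 per arm), about 50% long-term suppression (about 15 v 15), two-sided 0.05.

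Assumptions:
- The two tailored arms are pooled (10 v 20).
- All 30 patients are evaluable.
- A t-test is used for each comparison.
- There is no true effect.
- The reading is shifted by d SDs in one label group. For pairs, d is in SDs of the within-patient difference.

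Formulas: the false-positive rate is P(|T| > c), with T noncentral t.
- Two groups: noncentrality = d / √(1/n₁ + 1/n₂), 28 df, c = 2.048.
- Pairs: noncentrality = d × √30, 29 df, c = 2.045.

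For 10 v 20, √(1/10 + 1/20) = 0.387. For 15 v 15, √(2/15) = 0.365. For pairs, √30 = 5.477.

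| Comparison | d | Noncentrality | False-positive rate |
|---|---|---|---|
| Strain, 10 v 20 | 0.1 | 0.258 | 5.7% |
| | 0.3 | 0.775 | 11.6% |
| | 0.5 | 1.291 | 23.9% |
| Scar, 15 v 15 | 0.1 | 0.274 | 5.8% |
| | 0.3 | 0.822 | 12.5% |
| | 0.5 | 1.369 | 26.2% |
| Slow v other sites, 30 pairs | 0.1 | 0.548 | 8.3% |
| | 0.2 | 1.095 | 18.5% |
| | 0.3 | 1.643 | 35.5% |

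With d = 0 every row returns 5%. The within-patient comparison is the most sensitive, because pairing turns a small consistent shift into a large test statistic.

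**The case against.** The strongest reply is that silence is not evidence of unmasked reading. Section 4c is a form item about blinding the trial, and N/A also answers items 4d to 4g. A reader might infer that the images will be read by people who know the arm and outcome, and that the secondary results will therefore be biased. The documents do not support that. They leave open who reads what, so the finding is an absent safeguard and not a demonstrated bias. This part of the objection stands.

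The sizes are also assumed. At 0.1 SD the group comparisons stay close to nominal (5.7-5.8%), so it would be wrong to say that any small shift invalidates them. For objective 1, the calculation concerns a difference in means, whereas the hypothesis is an intermediate IIR band. It therefore does not show that bias would produce that banded pattern. Both limits stand.

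Other replies are weaker:

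- Operators cannot be blinded to the lesions they make, but that does not prevent masked measurement later.
- Section 4a restricts the file linking research IDs to patients. That is a confidentiality rule; it does not keep arm, rhythm or electrogram labels from an image reader.
- IIR and strain are numerical, but the steps that produce them are not stated to be automated.
- These are secondary analyses in a preliminary study. That limits the weight of the point, but section 7c still tests at 0.05 and section 7c also expects meaningful comparisons from this cohort.

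**Conclusion.** The point holds as an absent safeguard. Blinding is N/A, no other section masks the MRI measurements, and all three secondary objectives depend on them. Whether bias would arise, and how much, cannot be learned from the documents. On the assumed shifts, the false-positive rate runs from near nominal (about 6% at 0.1 SD) to 24-26% at 0.5 SD in the between-patient comparisons. It runs from about 8% at 0.1 SD to about 36% at 0.3 SD for 30 pairs. These figures rest on full follow-up, t-tests and pooling of the tailored arms, and they show sensitivity only. A change is worth making because it is cheap and because no later analysis can replace it. The point concerns secondary outcomes and does not touch safety.

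**What to change.** Replace N/A in section 4c with a short statement that operators and patients are not blinded (if that is the intention) but MRI measurements are masked, using the existing analysts:

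1. Align the electroanatomic map to the baseline LGE-MRI on anatomy, with conduction labels and LGE intensity hidden. Lock the alignment before extracting IIR at slow-conduction and other sites.
2. Read 12-month LGE from files coded by research ID, without rhythm outcome or arm.
3. Measure strain once, after the 12-month scan, with both scans coded, undated, in random order and without arm. Strain then needs no separate baseline reading.
4. Release arm and rhythm outcome only after the readings are locked. Where possible, have each patient's readings done by team members who did not review that patient's rhythm strips or prepare that patient's ablation map.

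The cost is one paragraph, coding of image files and some division of work within the team. Research IDs already exist, and no visit or procedure is added. In a small single-centre team the division of roles may not always be achievable, hence the qualifier in step 4. Arm masking of 12-month LGE is partial, because additional lesions may be visible. Masking to rhythm outcome and conduction labels remains feasible, and those are the labels for objectives 1 and 2.

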Comparison variables will be presented as means \pm SD, and categorical variables as numbers and percentages. Differences between treatment groups will be assessed using the Pearson Chi-square test and the Wilcoxon rank-sum test. Survival curves for time to event analysis will be estimated using the Kaplan-Meier method, and the differences between the curves will be tested for significance with the log-rank statistic. Weekly event rates will be calculated by dividing the event rate by the maximum follow-up period in each arm of the Kaplan-Meier analysis. Hazard ratios will be calculated by univariate and multivariate analysis using the Cox proportional-hazards regression model. When comparing MR image characteristics as well as LA function between pre and post-ablation imaging, the Student's t-test will be using for comparison of the means. All statistical testing will be 2-tailed. Results will be considered statistically significant at a level of $p < 0.05$.

- d. Early stopping rules. N/A

8. Risks

- a. Medical risks, listing all procedures, their major and minor risks and expected frequency.

As discussed above, all procedures except the post-ablation MRI is part of the standard clinical care. In addition, groups reporting their experience with substrate-based ablation have not encountered increased complications compared to the conventional ablation procedure (Narayan et al., 2012). In addition, there is no data suggesting any health hazard associated with magnetic field exposure (Schenck, 2000). All patients with pacemakers, implanted defibrillators or electronic/metallic devices, shrapnel and other metals such as metal in the eyes will be excluded.

Gadolinium chelates used as intravenous contrast media in MRI are considered safe and do not exhibit the nephrotoxicity associated with iodinated media. The injection of contrast intravenously is not painful, but

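### Section 7b hypothesises that slow conduction lies within an IIR band of 0.9-1.6, but the stated comparison uses neither limit and so does not separate being in the band from having a higher IIR

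*Combined protocol and SAP*

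**What the plan says.** Section 7b (Secondary outcome variables) hypothesises that sites with slow conduction in sinus rhythm "are detectable as sectors with intermediate LGE intensity [image intensity ratio (IIR) 0.9-1.6] on LGE-CMR". This is an interval with a lower and an upper limit. Slow-conduction sites are to be co-registered "with pre-procedural LGE-CMR for 30 patients", and the analysis is then one sentence: "We will then compare the baseline image intensity ratio of sites with slow conduction versus other sites".

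On the data available, 7b says that "the spatial coordinates and electrogram characteristics of >200 intra-cardiac points are sequentially sampled and saved". The next hypothesis in 7b treats the zone above the upper limit as a category of its own: AF suppression at one year is expected to be "associated with the presence of IIR>1.6 at the 1-year LGE-CMR in sectors where slow conduction was observed at baseline".

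Section 7c assigns no test to the slow-versus-other comparison. Chi-square and Wilcoxon tests are given for treatment groups. For pre- versus post-ablation imaging, "the Student's t-test will be using for comparison of the means". All tests are two-tailed at 0.05.

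**The concern.** The hypothesis is about membership of a band; the comparison, read plainly, is about level. The sites outside the band can lie below 0.9 or above 1.6, on opposite sides of it, so a difference in mean or rank does not map onto being inside or outside. Two-tailed testing does not help, because it asks higher or lower.

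Two errors are possible. If slow sites lie mainly above 1.6, their IIR will be higher than elsewhere and the result could be taken as support. If the other sites include both low and high tissue, a real concentration of slow sites in the band could average out to almost no difference.

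At stake is the IIR hypothesis in 7b. The one-year hypothesis that follows uses the same slow-conduction sectors, and Sections 1 and 11 present the 30-patient data as preliminary to a planned 300-patient trial.

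**Working it through.** **What can be reproduced.** The plan gives no SD, effect size, power or baseline distribution for the IIR comparison, so there is no planned figure to reproduce. The limits 0.9 and 1.6, the 30 patients and the 200 or so points per patient come from 7b, and alpha 0.05 two-tailed from 7c. All class shares, class means and outer IIR limits below are assumptions chosen to show the mechanism.

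**Hand calculation.** Assume class-mean IIRs of 0.7 (<0.9), 1.25 (0.9-1.6) and 1.9 (>1.6). Mean IIR is the sum of share × class mean. P(slow > other) is the chance that a random slow site falls in a higher class than a random other site, with ties counted half; this is the quantity behind a rank test.

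*Case (a), no band effect.* Shares in <0.9 / 0.9-1.6 / >1.6: slow 30/15/55%, other 70/15/15%.
- Band share: 15% v 15%.
- Mean, slow: 0.30×0.7 + 0.15×1.25 + 0.55×1.9 = 1.44.
- Mean, other: 0.70×0.7 + 0.15×1.25 + 0.15×1.9 = 0.96.
- P(slow > other): 0.15×0.70 + 0.55×0.85 + 0.5×(0.21 + 0.0225 + 0.0825) = 0.73.

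The level comparison looks positive with no difference in band share. The slow-site mean of 1.44 even falls inside 0.9-1.6, although only 15% of slow sites do, so a mean ± SD summary would not expose the problem.

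*Case (b), strong band effect.* Slow 10/80/10%, other 50/10/40%.
- Band share: 80% v 10%.
- Mean, slow: 0.10×0.7 + 0.80×1.25 + 0.10×1.9 = 1.26.
- Mean, other: 0.50×0.7 + 0.10×1.25 + 0.40×1.9 = 1.24 (1.235).
- P(slow > other): 0.80×0.50 + 0.10×0.60 + 0.5×(0.05 + 0.08 + 0.04) = 0.545.

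The level comparison is close to null although the band effect is large.

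**Simulation at the trial's size.** 1000 runs; 30 patients; 200 points each, 20% of them slow (assumed); IIR uniform within 0.5-0.9, 0.9-1.6 and 1.6-2.2 (outer limits assumed); class shares varying between patients (Dirichlet, concentration 15). Each patient contributes one slow-minus-other difference, tested by a two-sided one-sample t-test at 0.05. The last two columns give the percentage of runs significant in the supporting direction.

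| Scenario | Slow shares (low/band/high) | Other shares | Mean IIR difference | IIR level | In-band share |
|---|---|---|---|---|---|
| A: band true, others mostly low | 20/70/10 | 60/30/10 | +0.22 | 100% | 100% |
| B: slow sites mainly >1.6 | 20/20/60 | 60/30/10 | +0.54 | 100% | 0% |
| B2: slow sites shifted to >1.6, band share equal | 20/30/50 | 60/30/10 | +0.48 | 100% | 3% |
| C: band true, others split | 15/70/15 | 42/30/28 | +0.06 | 54% | 100% |
| C2: band true, others often >1.6 | 20/70/10 | 35/30/35 | -0.08 | 0% | 100% |

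In B the in-band test was significant against the hypothesis in 87% of runs. In C2 the level test was significant in the wrong direction in 75%.

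**The case against.** The strongest reply is that the sentence is under-specified rather than wrong. It names no summary measure, test or direction. Section 7c also lists chi-square tests and percentages, which an in-band comparison could use, although it ties chi-square to treatment groups. A categorical analysis is therefore not ruled out. This stands, and it is why the point is limited to the plain reading. It does not remove the point: the limits appear in the hypothesis and nowhere in the analysis, so the summary could be chosen after the data are seen.

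Three stronger conclusions are tempting, and the documents do not support them.
- A reader might infer that the plan *would* report slow conduction in dense scar as confirmation. No success criterion is stated, and slow sites concentrated above 1.6 would contradict the hypothesis on its face. The supportable word is could.
- A reader might infer that secondary objective 1 goes unanswered. Section 2 words it descriptively and names no band, so an IIR comparison does address it. Only the hypothesis in 7b lacks a matching test.
- A reader might equate baseline IIR above 1.6 with the tissue ablated in the second arm, or IIR below 0.9 with normal tissue. Section 4a describes that arm as "PVI plus targeting of dense LGE sites, which are confirmed on bipolar mapping to have voltage <0.1 mV", with no IIR cut-off; 7b uses the zone above 1.6 only for the one-year scan; nothing labels tissue below 0.9.

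It is also fair to say that the figures are hypothetical. Case (a) puts 55% of slow sites above 1.6 and case (b) puts 40% of other sites there; both are strong assumptions. In scenario A the two analyses agree.

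**Conclusion.** The point holds as a mismatch between hypothesis and stated analysis. It rests on the text of 7b and on reading a comparison of IIR as a comparison of its level; it does not depend on the assumed distributions. Its size does. Under those assumptions the level comparison was supportive in 100% of runs when slow sites lay mainly above 1.6, and in only 0-54% when the band hypothesis was true but the other sites included much tissue above 1.6. The in-band share gave 0-3% and 100% in the same settings. The two agree when other sites are mostly below 0.9 and few slow sites exceed 1.6. The documents give no baseline IIR distribution, so which setting applies cannot be judged from them.

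This concerns a secondary, mechanistic aim in a pilot. The primary comparison of time to recurrence is unaffected. It is worth correcting before analysis because the correction is nearly free.

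**What to change.** In 7b, replace the comparison sentence with the following elements:
- Classify each co-registered site or sector (state which) as IIR <0.9, 0.9-1.6 or >1.6.
- Make the test of the hypothesis the within-patient difference in the share lying in 0.9-1.6 between slow-conduction and other sites. Account for the clustering of more than 200 points per patient, either with one difference per patient or with a model that has a patient random effect or GEE.
- Report the full three-class distribution for both groups, including slow sites above 1.6, so that a shift into the upper class is visible.
- Keep the IIR-level comparison as descriptive.

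A stricter rule, requiring the proportion of sites that are slow to be higher in the band than in both outer classes, is not advised as the main test. Suppose 20% of sites are slow, with slow 10/80/10% and other 60/38/2%. The band share is 80% v 38%, a clear band effect. Yet the proportion slow is 0.16/(0.16 + 0.304) = 34% in the band and 0.02/(0.02 + 0.016) = 56% above 1.6, so the rule would reject it because of a sparse class.

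The cost is a change of wording; the points, scan and limits stay the same. Dichotomising at the band loses some information, and the class above 1.6 may hold few sites in some patients.
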